#### **8.3.2.2. Abuse, Misuse, or Medication Error**

Abuse is the persistent or sporadic, intentional excessive use of the study treatment which is accompanied by harmful physical or psychological effects.

A medication error is any preventable incident that may cause or lead to inappropriate study treatment use or patient harm while the study treatment is in the control of the health care professionals or patients. Such incident may be due to health care professional practice, product labeling, packaging and preparation, procedures for administration, and systems, including the following: prescribing, order communication, nomenclature, compounding, dispensing, distribution, administration, education, monitoring, and use.

All occurrences of abuse, misuse, or medication error with any study treatment are to be recorded on an SAE report form and sent to Karyopharm Pharmacovigilance, regardless of whether or not an AE or SAE has occurred due to the abuse, misuse, or medication error. If the abuse, misuse, or medication error is associated with an SAE, the SAE report form must be submitted to Karyopharm Pharmacovigilance within 24 hours of awareness. If there is no AE or SAE, the report must be submitted within 24 hours of awareness.

## 9. STATISTICAL CONSIDERATIONS

A statistical analysis plan (SAP) will be finalized prior to database lock. Any changes from the statistical analyses described in this document will be described in the SAP, and any deviation from the final SAP will be described in the final report.

### 9.1. General Considerations

Tabulations will be produced for appropriate demographic, baseline, efficacy, and safety parameters.

For categorical variables, summary tabulations of the number and percentage of patients within each category (with a category for missing data) of the parameter will be presented.

For continuous variables, the number of patients, mean, median, standard deviation, minimum, and maximum values will be presented.

#### 9.1.1. Procedures for Handling Missing Data

For AEs, missing dates will not be imputed; however, if partial dates are available, they will be used to assess if the AE occurred during the treatment period. Missing severities of AEs will not be imputed and will be considered missing in any tabulations of AE severity. If an AE is missing a response to the question regarding relationship to treatment, the event will be considered to be related.

### 9.2. Sample Size Determination

Approximately 247 patients CCI

### 9.3. Populations for Analyses

The intent-to-treat (ITT) population will consist of all patients who are randomized in the study with confirmed SARS-CoV2 infection under protocol version 6.0 and above, regardless of whether or not they receive study treatment.

The all-treat (AT) population will consist of all patients who took at least one dose of study treatment on this study and have confirmed SARS-CoV2 infection.

### 9.4. Statistical Analyses

Summary tabulations will be provided for disposition, demographic, baseline, efficacy, and safety data as noted in the following sections.

This section is a summary of the planned statistical analyses of the primary and secondary endpoints.

#### 9.4.1. Efficacy Analyses

Efficacy analyses will be performed in ITT population. If the primary endpoint, (Day 14 OSI), is significant, the 4 key secondary endpoints will be sequentially tested in the order listed below. If

any null hypothesis is not rejected in this sequence of tests, formal sequential testing will be stopped and the analyses of any endpoints thereafter will be nominal only.

- Time to recovery defined as improvement from baseline score of 3 to  $\geq 4$  or from a baseline score of 4 to  $\geq 5$
- Proportion of patients with at least a 2 point improvement (increase) in the Ordinal Scale from baseline to Day 7.
- Proportion of patients with at least a 1 point improvement (increase) in the Ordinal Scale from baseline to Day 7
- Proportion of patients with at least a 1 point improvement (increase) in the Ordinal Scale from baseline to Day 14.
- Time to an improvement of 2 point using WHO Ordinal Scale Improvement (TTCI-2)
- Time to clinical improvement (TTCI-1): defined as the time from randomization to an improvement of 1 point on the Ordinal Scale
- Overall Death rate on Day 28 (DR)
- Rate of mechanical ventilation (RMV)

The difference in binary endpoints between treatment arms will be calculated with a 95% confidence interval (CI). Comparison of these endpoints between the 2 treatment arms will be performed using the Cochran-Mantel-Haenszel (CMH) test stratified by the randomization stratification factors. The CMH estimate of the odds ratio and its 95% CI and the p-value for testing the treatment difference will be reported.

The analysis of time to event endpoints will be performed by treatment arm based on a log-rank test. The median will be estimated with a 95% CI for each treatment arm using the Kaplan-Meier method. Hazard ratios with the associated 95% CI will be estimated by a stratified Cox proportional hazards model, using Efron's method of tie handling, with treatment as the factor. The strata will be the same stratification factors used for randomization.

Analyses of all other secondary endpoints will be nominal only. Details will be specified in the SAP.

#### **9.4.2. Safety Analyses**

Safety analyses will be based on the reported AEs and other clinical information.

Safety analyses will be performed in AT population.

The safety and tolerability of selinexor will be evaluated by means of drug-related AE reports, physical examinations, and laboratory safety evaluations. The grading of the severity of the AEs will be done according to CTCAE, v.5.0. Investigators will provide their assessment as either the AE is related or not related to study drug.

Treatment-emergent AEs, SAEs, AEs of at least Grade 3 in severity, related AEs, and AEs leading to withdrawal of treatment will be summarized by cohort and in the overall safety population. Treatment-emergent AEs will be those that start or worsen on or after the first day of study treatment, through 30 days after last dose. Related AEs will be those with an Investigator determination of related to study drug.

### **9.4.3. Pharmacokinetic Analysis**

Plasma samples will be analyzed via a validated HPLC/MS-MS method for plasma selinexor concentration. Selinexor  $C_{max}$  and  $C_{trough}$  data will be summarized. Selinexor concentration data might also be analyzed using a population PK modeling approach if deemed necessary. Details of the population PK analysis, including software, post-processing and statistical analysis, will be outlined in a separate Data Analysis Plan to be completed prior to database lock.

### **9.4.4. Pharmacodynamic Analysis**

Plasma proteins will be assessed and quantified by immunoassays and multiplex assays when possible in a central lab.

### **9.4.5. Viral Analysis**

Viral testing will be assessed and quantified.

## **9.5. Criteria for Stopping the Study**

The criteria to halt the study will depend on the number of patients enrolled at the time of the analysis as described below:

- A. If the overall number of patients enrolled is  $\leq 60$  patients, the study will be halted if any 1 of the following conditions are met at an IA or Data Safety Monitoring Board (DSMB) meeting:
  - 1. The absolute difference in the death rate in the treatment arm versus the control arm is  $>30\%$
  - 2. The absolute difference in the need for invasive ventilation in the treatment arm versus the control arm is  $>30\%$
  - 3. The absolute difference in the rate of Grade 3 or 4 nausea or vomiting in the treatment arm versus the control arm is  $>20\%$
- B. If the overall number of patients enrolled is  $>60$  patients, the study will be halted if any 1 of the following conditions are met at an IA or DSMB meeting:
  - 1. The absolute difference in the death rate in the treatment arm versus the control arm is  $>20\%$
  - 2. The absolute difference in the need for invasive ventilation in the treatment arm versus the control arm is  $>20\%$
  - 3. The absolute difference in the rate of Grade 3 or 4 nausea or vomiting in the treatment arm versus the control arm is  $>20\%$
- C. If the overall number of patients enrolled is  $>120$  patients, the study will be halted if any 1 of the following conditions are met at an IA or DSMB meeting:
  - 1. The absolute difference in the death rate in the treatment arm versus the control arm is  $>10\%$
  - 2. The absolute difference in the need for invasive ventilation in the treatment arm versus the control arm is  $>10\%$

3. The absolute difference in the rate of Grade 3 or 4 nausea or vomiting in the treatment arm versus the control arm is  $>10\%$

In addition, each IA includes a futility analysis which will determine if there is no significant improvement in the ordinal score in the treatment arm compared with the control arm.

## 9.6. Interim Analyses

The first IA occurs 14 days after approximately 74 patients are randomized. This IA is for futility only. The futility boundary p-value will be calculated using the Lan DeMets spending function with the O'Brien-Fleming type of boundary based on the actual number of patients who have completed 14 days on study at the time of the IA.

The second IA happens 14 days after approximately 124 patients are randomized. This IA is for futility and sample size reestimation. An unblinded sample size re-estimation (SSR), is planned to be performed at this IA. The unblinded SSR will be based on the method of conditional power (CP). It is defined as the probability to detect a statistically significant difference for the primary endpoint at the end of study given the current data observed at this IA, assuming this interim trend continues. The CP will be calculated for the primary endpoint at this IA using East software with CHW method (Cui 1999).

The odds ratio and associated p-value will be obtained for the primary endpoint OSI between two arms based on the observed data at this IA, then the CP will be calculated using East. The calculated CP will be assigned to one of the 3 zones:

1. favorable ( $CP \geq 80\%$ )
2. promising ( $30\% \leq CP < 80\%$ )
3. unfavorable ( $CP < 30\%$ )

The original planned total sample size of approximately 247 patients will be increased to achieve the targeted power of 80%, up to a maximum of 371 patients when the conditional power is in the promising zone. If the CP is  $<30\%$ , the trial may be stopped for futility (non-binding). Otherwise, if the CP is  $\geq 80\%$  the total sample size will remain at 247 patients, and the trial continues as planned.

If the trial is not stopped at IAs and sample size is not changed based on the second IA, enrollment will continue until approximately 247 patients are enrolled, the final analysis will happen when all enrolled patients have had the chance to have the Day 14 OSI assessed.

At the interim analyses, primary efficacy outcome and selected safety outcomes will be reviewed by the Data Safety Monitoring Board (DSMB) to determine if the trial will be stopped for futility, adjust the sample size, or continue as planned.

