#### **6.4. Blinding**

The site investigators and patients are blinded to treatment assignment during the conduct of the study. All study staff will be blinded to the treatment assignments and study drug will be administered in a blinded manner.

Unblinding of treatment assignments should be undertaken for safety reasons when it is essential for effective treatment of the patient.

Unblinding is performed using the IRT. When the investigator contacts the IRT to unblind a patient, he/she must provide the requested patient identifying information and confirm the necessity to unblind the patient. The Investigator will then receive details of the drug treatment for the specified patient.

The entire study population will be unblinded at the end of the study and the unblinding information will be shared with each study site.

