#### **6.6. End of Study**

End of Study will occur when the last patient has completed the 30-day Safety follow up period (after their last dose of study treatment), has withdrawn consent or has died, whichever comes first.

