**Table 6: Efficacy Endpoints and Definitions**

Endpoint	Definition
Primary Endpoint	
Day 14 Ordinal Scale improvement (OSI2-14)	Proportion of patients with at least a 2 points improvement (increase) in the Ordinal Scale by Day 14. Baseline score is defined as the last score measured before first dosing. The improvement is assessed between the baseline score and the latest score on or before Day 14, End of study (EoS) date, or database cut date, whichever occurs first.
Key Secondary Endpoints	
Time to an improvement of 2 points using Ordinal Scale (TTCI-2)	The time from randomization to an improvement of 2 points on the Ordinal Scale. For patients who didn't achieve clinical improvement of 2 points, 
 
If no death event by Day 28, they will be censored on the last contact date, on or before Day 28, EoS date, or database cut date, whichever occurs first.
 
 If they died by Day 28, they will be censored on Day 28.
Overall death rate on Day 28 (DR-28)	Proportion of patients died on or before Day 28.
Rate of mechanical ventilation (RMV)	Proportion of patients who ever used invasive mechanical ventilation or ECMO during the hospital stay.
Time to mechanical ventilation (TTMV)	Time to the first use of mechanical ventilation. For patients who never used mechanical ventilator, the censoring date is defined as the death date or last contact date (if no death), on or before EoS or database cut date, whichever occurs first.

Additional Secondary Endpoints	
Time to recovery (TTR)	Time to improvement from baseline score of 3 to $\geq 4$ or from a baseline score of 4 to $\geq 5$ by Day 28. For patients who didn't achieve recovery, the censoring rule will be the same as that in TTCI-2.
Day 7 Ordinal Scale 2 points improvement (OSI2-7)	Proportion of patients with at least a 2 points improvement (increase) in the Ordinal Scale from baseline to Day 7. The improvement is assessed between the baseline score and the latest score on or before Day 7, End of study (EoS) date, or database cut date, whichever occurs first.
Day 7 Ordinal Scale 1 point improvement (OSI1-7)	Proportion of patients with at least a 1 point improvement (increase) in the Ordinal Scale from baseline to Day 7. The improvement is assessed the same as in OSI2-7.

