### 7.1.1 Sensitivity Analyses

In a sensitivity analysis for OSI2-14, the assessment of 2 points improvement will be conducted with the baseline score defined as the last score before first dosing, or a lower score within 24 hours of randomization, whichever is lower.

The classification of whether a score can be considered as within 24 hours of randomization will be determined based on the date and time of randomization and score assessment. If there is partial date/time that make it impossible to determine whether the difference is within 24 hours, to be conservative, the score will be considered to be outside the 24-hour window.

Specifically,

- If the date of lower score is missing, it will be categorized as “outside 24 hours”.
- If the date of lower score is not missing, but hour is missing:
  - It will be categorized as “within 24 hours” if the lower score is measured on the same day of randomization.
  - It will be categorized as “outside 24 hours” if the lower score is measured on subsequent day of randomization.
- If both date and hour are not missing, but minute is missing:
  - It will be categorized as “within 24 hours” if lower score is on same day or subsequent day of randomization and hour is earlier than the hour in randomization time.

It will be categorized as “outside 24 hours” if lower score is on subsequent day of randomization and hour is the same or later than the hour in randomization time.

In the ITT population, the first approximately 50 patients were randomized with an allocation ratio of 2:1, the other patients in the ITT population will be randomized with an allocation ratio of 1:1. The switch of allocation ratio was due to an administrative reason and independent of patient characteristics and thus is not expected to cause any confounding bias. In a sensitivity analysis for OSI2-14, the CMH test will be conducted

stratifying by the randomization stratification factors and the period for the allocation ratio to assess robustness of results.

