## 7.2 Analyses of Secondary Efficacy Endpoints

### 7.2.1 Analyses of Key Secondary Efficacy Endpoints

If the primary endpoint, OSI2-14, is significant in ITT population, the following key secondary endpoints in ITT population will be sequentially tested in the order listed below. If any null hypothesis is not rejected in this sequence of tests, formal sequential testing will be stopped and the analyses of any endpoints thereafter will be nominal only.

- Time to clinical improvement (TTCI-2)
- Overall Death rate on Day 28 (DR-28)
- Rate of mechanical ventilation (RMV)
- Time to mechanical ventilation (TTMV)

For binary endpoints (DR-28, RMV), the difference in rates between treatment arms will be calculated with a 95% confidence interval (CI). Comparison between 2 treatment arms will be performed using the Cochran-Mantel-Haenszel (CMH) test stratified by the randomization stratification factors. The CMH estimate of the odds ratio and its 95% CI and the p-value for testing the treatment difference will be reported.

For time to event endpoints (TTCI-2, TTMV), the number and percentage of patients with the corresponding events will be reported. Median event times with 95% CIs will be estimated by Kaplan-Meier (KM) method for each treatment arm. KM curves by treatment arms will be provided.

The following analysis stratified on randomization strata will be performed:

- Log-rank test stratified to compare the event times between treatment arms

- Hazard ratios of treatment effect with 95% CI estimated by Cox proportional hazards model with Efron's method of tie handling

Non-stratified log rank test and Cox proportional hazards model will be performed as sensitivity analyses.

The Kolmogorov-type Supremum test will be conducted to assess the validity of the proportion hazards assumption in all fitted Cox proportional hazards models. If there is evidence for a violation of the proportional hazards assumption, interaction terms between time-dependent terms and treatment variable (selinexor vs. placebo) will be added to assess time-varying treatment effects.

In sensitivity analysis for RMV, analyses will be conducted with patients who ever used one of the respiratory assistances as below:

- Non-invasive positive pressure mechanical ventilation (CPAP/BiPAP)
- High-flow nasal cannula
- Invasive mechanical ventilation
- Extracorporeal membrane oxygenation (ECMO)

For TICI-2, sensitivity analyses will be performed in the same manner as OSI2-14.

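### The final analysis is triggered at the last patient's Day 14, but the tested Day 28 death rate has no rule for patients short of Day 28, and unblinding and database lock are set for end of study

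*Protocol*

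**What the plan says.** - **Trigger.** Under Protocol 9.6, if neither interim stops the trial and the second leaves the sample size alone, enrolment runs to about 247 and "the final analysis will happen when all enrolled patients have had the chance to have the Day 14 OSI assessed". The same section allows the sample size to be "increased to achieve the targeted power of 80%, up to a maximum of 371 patients", but gives no trigger for that branch.
- **Dosing.** The protocol synopsis and section 5.1 give two weeks of study drug. Patients who qualify may continue, with doses up to Day 26.
- **Blind and lock.** Protocol 6.4 blinds investigators, patients and study staff while the study runs. It adds: "The entire study population will be unblinded at the end of the study". Section 6.6 defines that point: "End of Study will occur when the last patient has completed the 30-day Safety follow up period", counted from the last dose. Section 10.4.4 locks the database at the conclusion of the study.
- **Tested endpoints.** SAP 7.2.1 says that if the primary is significant, "the following key secondary endpoints in ITT population will be sequentially tested in the order listed below": TTCI-2, DR-28, rate of mechanical ventilation (RMV) and time to mechanical ventilation (TTMV). Protocol 9.4.1 has a longer list in a different order, which also contains DR-28 and TTCI-2.
- **Definitions.** SAP Table 6 defines DR-28 as "Proportion of patients died on or before Day 28", and SAP 7.2.1 compares it by a stratified CMH test. TTCI-2 and TTMV have censoring rules that refer to a database cut date. RMV covers the hospital stay.
- **Missing data.** SAP 4.4 imputes nothing unless stated. SAP 6.1 tabulates patients still on treatment.

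**The concern.** The trigger fits the primary endpoint but not two of the endpoints tested after it. A by-arm analysis at the last patient's Day 14 also comes before the lock and the unblinding that other sections place at end of study, and no section reconciles the two.

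Two things are at stake. First, DR-28 is a formally tested mortality endpoint, and in the SAP order its p-value decides whether RMV and TTMV are formally tested. If it is computed at the trigger, some patients have unknown Day 28 status. Neither document says how to count them, whether the test is repeated later, or which p-value would govern.

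Second, arm-level results could exist while late patients are still being dosed, scored and assessed for adverse event causality. Causality is the investigator's judgement (Protocol 8.1.3), and continued dosing depends partly on it. The documents describe no firewall for the final analysis. Protocol 10.5 deals with DSMB review.

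**Working it through.** **Stated sample size.** Protocol 9.2 gives "Approximately 247 patients", but the inputs to that figure are redacted, so it cannot be reproduced. The point does not depend on it except as a denominator.

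**Step 1: the last patient's calendar at the trigger (Day 14).**
- To Day 28: 28 − 14 = 14 days.
- To the last possible extension dose: 26 − 14 = 12 days.
- To end of study, if that patient continues to Day 26: 26 + 30 = Day 56, and 56 − 14 = 42 days. Counting instead from end of treatment on Day 28 with the +2-day visit window in the schedule of assessments: 28 + 32 = Day 60, and 60 − 14 = 46 days.
- To end of study, if that patient stops after the Day 12 dose: 12 + 30 = Day 42, and 42 − 14 = 28 days.

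On every route the trigger comes before end of study.

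**Step 2: which tested endpoints are incomplete at the trigger.**

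| Endpoint | Horizon | Rule at a data cut |
|---|---|---|
| Primary (Day 14, 2 points) | Day 14 | complete |
| TTCI-2 | Day 28 | living patients without improvement are censored by the cut |
| DR-28 | Day 28 | none |
| RMV | hospital stay, no fixed day | none stated |
| TTMV | end of study or cut | censored by the cut |

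The Day 7 and Day 14 proportions in the longer list of Protocol 9.4.1 are also complete.

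**Step 3: patients short of Day 28.** The documents give no accrual rate. Assume uniform accrual of 247 patients over T weeks. The number short of Day 28 is 2 × 247 / T, less any who have already died.
- T = 12: 20.6 per week, about 41 patients (16.7%).
- T = 20: 12.35 per week, about 25 patients (10.0%).
- T = 30: 8.2 per week, about 16 patients (6.7%).

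A wider assumed range of 1.5 to 9 months gives about 76 to 13 patients (31% to 5%). If the sample size rises to 371 at the same weekly rate, the counts are unchanged and the shares fall, for example 41/371 = 11%.

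**Step 4: deaths not yet seen.** Assume that 40% of Day 28 deaths fall on Days 15–28, spread evenly, so that about half of these are still to come in the late patients. If those patients are counted as non-deaths, the share of Day 28 deaths missed is 0.40 × 0.5 × fraction short of Day 28:
- 0.20 × 6.7% = 1.3%
- 0.20 × 16.7% = 3.3%

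At an assumed Day 28 mortality of 10–15% (about 25 to 37 deaths in 247), that is 0.013 × 25 = 0.3 to 0.033 × 37 = 1.2 deaths over both arms. A harsher pairing, with half of the deaths after Day 14 and 31% of patients short of Day 28, gives 0.5 × 0.5 × 31% = 7.8%.

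**Step 5: the alternative handling.** If unknown status is treated as missing and dropped, the analysed set falls to between 247 − 41 = 206 and 247 − 16 = 231. It is then no longer full ITT. Early deaths among late patients would stay in while their living contemporaries drop out.

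**The case against.** The strongest reply has four parts.

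**The blind.** Section 6.4 protects sites and patients, and shares assignments with sites only at end of study. A group-level result does not reveal one patient's arm. Protocol 9.6 itself plans an unblinded analysis at about 124 patients while the trial continues, and the study is labelled single-blind. This stands against any claim that the blind is bound to fail. It does not supply the missing statement of who may see results between the final analysis and end of study.

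**The lock.** Section 10.4.4 puts lock at the conclusion of the study. Section 9.6 might therefore only mark when the primary matures, with the analysis run on complete data later. That reading is possible. However, the SAP's database cut date and its count of patients still on treatment point to an early cut. Where both readings are open, the text needs to choose.

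**Existing rules.** Cut-date censoring already covers TTCI-2 and TTMV. That is correct, and it leaves DR-28 as the main gap.

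**Size.** The shift is small and rests on assumed accrual and death timing. SAP 7.1.1 says that after about the first 50, "the other patients in the ITT population will be randomized with an allocation ratio of 1:1", so truncation should fall about equally on the arms. In the SAP order, DR-28 is tested only if the primary and TTCI-2 succeed. An early readout is also a legitimate sponsor choice in a pandemic Phase 2 trial. All of this stands, and it limits the seriousness of the point. It does not justify testing a mortality endpoint with no rule for incomplete follow-up when two more weeks would complete it.

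**Conclusion.** The mismatch is real and worth correcting. As written, Protocol 9.6 allows DR-28 to be tested while roughly 7–17% of the ITT population is short of Day 28 (accrual of 30 to 12 weeks, assumed). It also allows arm-level results to exist 28 to 46 days before end of study, depending on the last patient's dosing. The likely shift in DR-28 is about 1–3% of deaths under the Step 4 assumptions, and up to about 8% under harsher ones. The primary endpoint is unaffected.

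A reader might infer more than the documents support:
- *The blind is lost for every late patient.* The documents do not say that results or assignments reach sites at the final analysis. The blind is unprotected in writing, no more.
- *Patients short of Day 28 count as alive.* Table 6 does not say so. The SAP's rule against imputation fits a missing category at least as well. The missed-deaths figure applies only if they are counted as non-deaths.
- *All patients are dosed to Day 26.* Extension is conditional.
- *Every tested key secondary runs to Day 28.* Only TTCI-2 and DR-28 do in the SAP sequence. RMV and TTMV have no Day 28 horizon, though follow-up for them would also be cut short.

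**What to change.** 1. **Protocol 9.6.** For both the unchanged and the increased sample size, set the data cut and final analysis when all ITT patients have reached Day 28, died or withdrawn. If the sponsor wants the primary at the last Day 14, hold at minimum the formal tests of TTCI-2 and DR-28 until the Day 28 cut. Every test after them in the sequence then waits too.
2. **SAP Table 6.** State how DR-28 treats a patient who withdraws or is lost before Day 28 with unknown vital status.
3. **Protocol 6.4, 6.6 and 10.4.4.** Reconcile these with the cut. Say that individual assignments and arm-level results are not released to sites or patients before end of study. Distinguish the data cut for the final analysis from the final lock, and report the 30-day safety follow-up as an update. This is needed even with a Day 28 cut, because adverse event follow-up continues after it.

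The cost is about 14 days' delay to the readout and a few sentences in the two documents. Sample size, alpha and the primary endpoint do not change. By the Day 28 cut the last scheduled dose (Day 26) has passed, so arm-level results would no longer exist during scheduled dosing.
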